STUDY PROTOCOL WITH STATISTICAL ANALYSIS PLAN

Study Title: Vaginal Breech Birth Management: serious mobile game design and evaluation for midwifery students

NCT Number: NCT05551611

Document Date: March 14, 2025

1. Background and Rationale

Vaginal breech birth (VBB) is now an infrequent clinical event; consequently, midwifery students have limited real-life learning opportunities. Serious games offer cost-effective, repeatable simulation experiences that can enhance knowledge acquisition. This study evaluates a bespoke mobile serious game designed to teach VBB management and compares it with traditional lecture-based instruction.

2. Aims

- To determine whether the serious mobile game improves short-term knowledge of VBB management compared with a traditional lecture.
- To compare knowledge retention at 14 days and 7 months post-intervention between groups.

3. Study Design

Prospective, parallel-group, randomised controlled quasi-experimental trial with pre-test/post-test assessments.

- **Setting:** Midwifery departments of two Turkish universities (Kocaeli University & Eskişehir Osmangazi University).
- **Duration:** February 2022 – December 2022 (follow-up to July 2023).

4. Study Population and Eligibility Criteria

Third-year midwifery students.

Inclusion:

- Completed “Normal Childbirth & Postpartum” course.
- Provide written informed consent.

Exclusion: Previous theoretical or practical training on breech presentation.

5. Interventions

5.1. Experimental Arm – “Game Group”

Students play the **Vaginal Breech Birth Management Serious Mobile Game** once ($\approx 30\text{--}45$ min) under supervised classroom conditions. Headphones supplied; individual play; no time limit.

5.2. Control Arm – “Lecture Group”

Traditional 45-min lecture covering identical VBB content, delivered by the same investigator with slides & discussion.

6. Outcome Measures

Type	Name	Description	Scale (range)	Direction
Primary	Vaginal Breech Birth Management Knowledge Test	47-item multiple-choice test assessing knowledge of trauma & management in VBB. Each correct answer = 1 point; Total score 0–47 . No subscales; higher scores = better knowledge/outcome.	0–47 scores on a scale	Higher = better

Assessments at baseline (pre-test), Day 0 (immediately after intervention), Day 14, and Month 7.

7. Sample Size & Power Calculation

Using Day 0 pilot means (Game=40.5 \pm 4.2; Control=37.8 \pm 5.1), $\alpha=0.05$, two-sided Mann–Whitney U, power=0.80 required **n=35 per group**. Allowing 10 % attrition, recruitment target set at 40 per group (total 80). Final analysed: Game=39; Control=40.

8. Randomisation and Allocation

Simple randomisation (1:1) using computer-generated list by independent statistician. Group assignment placed in sealed opaque envelopes; opened by researcher immediately before session.

9. Data Collection Procedures

Knowledge test administered on paper. Unique codes used instead of names. Data entered twice into SPSS 20.0; discrepancies resolved by audit.

10. Statistical Analysis Plan (SAP)

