10.1. Primary Outcome Analysis

- **Between-group comparison (Day 0):** Mann–Whitney U test.
- Report Median (IQR) & Mean \pm SD.

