10.3. Assumptions & Checking

- Normality checked via Shapiro–Wilk; non-normal distribution anticipated \Rightarrow non-parametric tests chosen.

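### The 35 per group in Section 7 does not follow from its printed inputs: under a normal shift model a two-sided Mann–Whitney test needs 51–52, and 35 gives about 64% power, not 80%

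*Combined protocol and SAP*

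**What the plan says.** Section 7 bases the sample size on pilot data for the primary outcome, the 0–47 knowledge test immediately after the session: "Using Day 0 pilot means (Game=40.5 \pm 4.2; Control=37.8 \pm 5.1". With alpha 0.05 it states that a "two-sided Mann–Whitney U, power=0.80 required n=35 per group". It then adds a margin for loss, "Allowing 10 % attrition, recruitment target set at 40 per group (total 80", and reports the outcome of recruitment: "Final analysed: Game=39; Control=40". Section 8 gives the allocation ratio: "Simple randomisation (1:1".

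Section 7 does not say what the ± values are, and it names no formula, software or score distribution for the calculation. Two other places bear on this. Section 10.1 asks for "Report Median (IQR) & Mean \pm SD" for the same outcome, which makes SD the natural reading of ±. Section 10.3 says "non-normal distribution anticipated" and gives this as the reason for rank-based tests, without naming a distribution.

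**The concern.** Section 7 presents 35 as the result of the inputs beside it. Apart from a score distribution, every input needed to check it is printed, and a standard calculation gives a number nearly half as large again. Even the t-test, which needs fewer participants than the Mann–Whitney test when scores are normal, does not come down to 35.

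The figure supports the claim of 80% power for the primary Day 0 comparison. If true power was nearer 70% at the numbers analysed, the chance of missing the planned 2.7-point difference was about 30% rather than 20%. A reader who trusts the 80% would take a non-significant Day 0 result as stronger evidence of no difference than it is.

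**Working it through.** **Inputs.** From Section 7: Game 40.5 ± 4.2, Control 37.8 ± 5.1, two-sided alpha 0.05, power 0.80, Mann–Whitney U; analysed 39 and 40. From Section 8: 1:1 allocation. Assumption: each ± value is an SD.

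**Effect size**
- Difference = 40.5 − 37.8 = 2.7
- Pooled SD = √[(4.2² + 5.1²)/2] = √[(17.64 + 26.01)/2] = √21.825 = 4.672
- d = 2.7/4.672 = 0.578

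**Attempt to reproduce 35 (n per group, two-sided, 80% power)**
- Normal approximation: 2(1.960 + 0.842)²/d² = 2 × 7.849/0.334 = 47.0
- t-test (noncentral t): 48.0
- Mann–Whitney, normal shift model: the noncentral t calculation with n multiplied by the asymptotic relative efficiency (ARE) 3/π = 0.955 gives 50.2, so 51
- Noether's formula: P(X>Y) = Φ(2.7/√(4.2² + 5.1²)) = Φ(2.7/6.607) = 0.6586; n = 7.849/[6 × (0.1586)²] = 52.0

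None gives 35.

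**Power at the stated and analysed sizes (Mann–Whitney, normal shift, ARE method).** 64.3% at 35/35 and 69.7% at 39/40. Simulation with the two printed SDs agrees: about 64% and about 69%.

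**Could rounding explain it?** Moving each of the four printed values by up to 0.05 changes the Mann–Whitney requirement only from 45.8 to 55.2, that is 46 to 56. Under the same model, 35 per group reaches 80% power only at d of about 0.70, a difference of about 3.25 points with these SDs.

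**Could the attrition step explain it?** No. 35/0.9 = 38.9, so 39, and the target was set at 40. That step is consistent; the gap lies in the 35.

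**Could a different setting explain it?**
- One-sided, normal shift: 39.5, so 40
- One-sided, logistic scores: 34.4, so 35; but Section 7 says two-sided
- Two-sided, logistic scores: 43.7, so 44
- Two-sided, Game SD 4.2 only: 40 under the normal model, and 35 only with logistic scores as well; this ignores the control SD
- Two-sided, Laplace (heavy-tailed) scores: 32 by ARE, but ARE flatters the test at this size. Simulated power is 79–80% at 35 and about 81% at 36, so about 36 are needed

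**Sensitivity to skew.** Scores simulated as integers on 0–47 with the printed means and SDs; tie-corrected two-sided Mann–Whitney; 20,000 runs per cell (Monte Carlo SE about 0.003):

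| Shape (skewness Game/Control) | Power 35/35 | Power 39/40 | n per group for 80% |
|---|---|---|---|
| Beta-binomial (−0.9/−0.7) | 64.5% | 70.3% | about 50 |
| Beta (−1.0/−0.8) | 65.6% | 71.1% | about 48–49 |
| 47 minus gamma (−1.3/−1.1) | 69.6% | 75.4% | about 44–45 |
| Reflected gamma, shape 1.5 (−1.6/−1.6) | 77.7% | 82.2% | about 37 |
| Reflected lognormal (−2.1/−1.7) | 79.6% | 84.6% | about 36 |

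Moderate left skew leaves power at 35 between 64% and 70%. Only strong skew or heavy tails bring it near 80%.

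**The case against.** The best counter-argument is that means and SDs do not fix the power of a Mann–Whitney test. Section 10.3 expects non-normal scores, so a normal shift model is the reviewer's benchmark and not the plan's. A two-sided calculation with a Laplace parent lands almost on 35, so the figure may come from a correctly run calculation with a setting that was never written down. That stands as far as it goes: 35 cannot be called impossible, and power at 39/40 runs from about 70% to 85% over the shapes examined. It does not rescue the text. Section 10.3 names no distribution and uses non-normality to choose the test, not as an input to the sample size. A Laplace shape is also hard to motivate for a test capped at 47 with means near 40. If that setting was used, it is the assumption that Section 7 leaves out.

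A second argument is that follow-up is over and the numbers are fixed, that the aim is superiority, and that nothing in the plan says a non-significant result will be read as equivalence. It is also fair that an effect estimate with a confidence interval says more about a finished trial than planning power does. These points limit the consequence and are the reason no change in size is asked for. The power claim is still printed beside the analysed numbers, where it invites the reader to rely on it.

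**Conclusion.** The concern holds. The stated 35 per group for 80% power cannot be obtained from the inputs in Section 7. Under a normal shift model the requirement is 51 to 52; 35 gives about 64% power, and the analysed 39/40 about 70%. This rests on reading ± as SD and on the normal shift model. The shortfall remains under moderate left skew and nearly disappears under strong skew or heavy tails, neither of which the documents state. So either the number is wrong or the assumption that produced it is missing; both are corrected in the same place. Confidence is high that 35 is not reproducible as printed, and lower on which of the two explanations applies. The validity of the Day 0 test is not affected. This should be fixed.

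**What to change.** Revise Section 7 in one of two ways.

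1. State the score distribution, sidedness, formula or software that produced 35, and label the ± values.
2. If that cannot be recovered, replace the claim with wording such as: *For the pilot inputs (mean ± SD), two-sided alpha 0.05 and a Mann–Whitney test under a normal shift model, 35 per group gives about 64% power and the analysed 39/40 about 70%; power depends on the assumed score distribution.* Adding the range of about 70% to 85% at 39/40 across the skewed and heavy-tailed shapes above would suit the non-normality expected in Section 10.3.

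In either case, interpret a non-significant Day 0 result against the restated figure and its assumption. The cost is wording only: no added enrolment and no change to the analysis, though the stated power may become less favourable.

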10.1. Primary Outcome Analysis

- **Between-group comparison (Day 0):** Mann–Whitney U test.
- Report Median (IQR) & Mean \pm SD.

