10.2. Secondary/Exploratory Analyses

- **Within-group change over time:** Friedman two-way repeated measures ANOVA (pre, Day 0, Day 14, Month 7). Post-hoc Dunn-Bonferroni pairwise tests.
- **Between-group at Day 14 & Month 7:** Mann–Whitney U.

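### The pre-test score is left out of all three between-group comparisons; the tests remain valid under randomisation but give up precision

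*Combined protocol and SAP*

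**What the plan says.** Section 6 defines one outcome, a 47-item test scored 0–47, and sets its schedule: "Assessments at baseline (pre-test), Day 0 (immediately after intervention), Day 14, and Month 7". Every student is therefore due a pre-test on the same scale as the outcome.

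The between-group analyses use the follow-up score alone:

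- Section 10.1 (primary): "Between-group comparison (Day 0): Mann–Whitney U test".
- Section 10.2 (secondary): "Between-group at Day 14 & Month 7: Mann–Whitney U".

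The pre-test enters one analysis in section 10.2, which is run inside each arm: "Within-group change over time: Friedman two-way repeated measures ANOVA (pre, Day 0, Day 14, Month 7"). No between-group change score, ANCOVA, rank ANCOVA or group-by-time model appears anywhere in section 10.

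The reason for the choice of tests is in section 10.3: "Normality checked via Shapiro–Wilk; non-normal distribution anticipated". Section 8 describes simple 1:1 randomisation from a computer-generated list, with no balancing on the pre-test. Section 7 already reports the numbers analysed: "Final analysed: Game=39; Control=40".

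**The concern.** Both aims in section 2 compare the groups, and the Friedman tests cannot answer either of them. The comparisons that can answer them ignore a baseline measurement of the same quantity that the trial already collects. Expected non-normality is a reason to use ranks. It is not a reason to drop the covariate, because a rank ANCOVA uses ranks and adjusts for the pre-test.

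If the pre-test predicts the later score, adjusting for it removes part of the residual variance and with it the part of the observed difference that comes from chance imbalance at baseline. Simple randomisation of about 80 students does nothing to limit that imbalance. The stake is precision: a wider interval and lower power in a trial that, on its own inputs, has less power than it planned.

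**Working it through.** **Inputs.** From section 7: pilot Day 0 means and SDs of 40.5 (4.2) for the game and 37.8 (5.1) for the lecture, two-sided alpha 0.05, planned power 0.80, stated n of 35 per group, and 39 and 40 analysed. Rho is not given, so 0.2, 0.3 and 0.5 are assumed to show a range.

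**The plan's own figure.**

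- Pooled SD = sqrt((4.2² + 5.1²)/2) = 4.672. Difference = 40.5 − 37.8 = 2.7. Standardised effect d = 2.7/4.672 = 0.578.
- Normal formula: n per group = 2 × (1.960 + 0.842)² / 0.578² = 47. The t-based answer is 48. Dividing by the Mann–Whitney efficiency of 3/π gives 50.
- The stated 35 is therefore not reproduced from two-sided inputs. That is a separate matter. It counts here only because it leaves power at 39/40 near 0.71 by formula, so precision is not in surplus.

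**Effect of adjustment.** Adjusting for the pre-test multiplies the residual variance by (1 − rho²).

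- Standard error of the unadjusted difference = 4.672 × sqrt(1/39 + 1/40) = 4.672 × 0.225 = 1.051 points. The 95% half-width is 1.991 × 1.051 = 2.09 points.
- The adjusted half-width is this multiplied by sqrt(1 − rho²).
- t-test power at 39/40 (noncentral t) = 0.718. ANCOVA power replaces d by d/sqrt(1 − rho²).
- Equivalent total n = 79/(1 − rho²).

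The rank-test rows are simulated with 6,000 runs per cell (Monte Carlo standard error about 0.006), with integer scores capped at 47.

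| Quantity at Day 0, 39 vs 40 | Unadjusted | rho 0.2 | rho 0.3 | rho 0.5 |
|---|---|---|---|---|
| Variance factor 1 − rho² | 1 | 0.96 | 0.91 | 0.75 |
| Mann–Whitney power (simulated) | – | 0.696 | 0.693 | 0.699 |
| Rank-ANCOVA power (simulated) | – | 0.712 | 0.732 | 0.804 |
| t-test, then ANCOVA power | 0.72 | 0.735 | 0.76 | 0.83 |
| 95% CI half-width (points) | 2.09 | 2.05 | 2.00 | 1.81 |
| Equivalent total n | 79 | 82 | 87 | 105 |

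A separate simulation of 8,000 runs gave 0.70 against 0.73 at rho 0.3 and 0.69 against 0.79 at rho 0.5.

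**Validity.** Simulated type I error at rho 0.3 and 0.5 was 0.056 and 0.049 for Mann–Whitney, 0.055 and 0.053 for rank ANCOVA, and 0.050 and 0.053 for ANCOVA with HC3 standard errors. All are close to 0.05, so the unadjusted test holds its level.

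**Chance imbalance.** One standard error of pre-test imbalance is 0.225 SD. It shifts the unadjusted Day 0 difference by rho × 4.672 × 0.225: 0.21, 0.32 or 0.53 points at rho 0.2, 0.3 or 0.5. The 95% range (1.96 times this) is ±0.41, ±0.62 or ±1.03 points, against a planned difference of 2.7. This is the same variance component as in the table seen another way, not an additional loss.

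**The case against.** The case for leaving the plan alone is that this is a choice and not an error. An unadjusted rank test of a randomised comparison is a legitimate primary analysis, and it is the test named in the sample-size section. Rho is unknown. It may well be low, because the exclusion criterion in section 4, "Previous theoretical or practical training on breech presentation", could leave pre-test scores low and narrowly spread. The larger gains need rho near 0.5, which nothing in the document supports. The plan specifies neither a t-test nor a confidence interval, so the rank-to-rank comparison is the relevant one. All the figures use Day 0 inputs, so nothing is quantified for Day 14 or Month 7. Finally, with the analysed numbers already reported, adjusted models added now cannot restore power to the primary test.

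Most of this stands as a limit on weight. The test is valid, the gain at rho 0.2 is about two power points, and the figures apply to Day 0 only. It does not remove the point. No reason is given for omitting the covariate, adjustment costs one degree of freedom if rho turns out to be near zero, and the pre-test is already scheduled for collection. An adjusted estimate in points with an interval would also add something that section 10.1 does not ask for.

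One caveat cuts the other way. Section 3 calls the design both randomised and quasi-experimental. If allocation were not in fact random as section 8 describes, leaving out the baseline would also raise a concern about bias.

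**Conclusion.** The concern holds, as a loss of precision and not a bias. None of the three between-group comparisons uses the pre-test, and the stated reason for non-parametric tests does not explain the omission. At Day 0, on the plan's pilot figures, moving from Mann–Whitney to rank ANCOVA would gain about 2, 4 or 10 power points at rho 0.2, 0.3 or 0.5. The loss is minor if rho is 0.2 or less and material from about 0.4 to 0.5. The conclusion rests on genuine randomisation, on an assumed range for rho, and on the pilot means and SDs. Rho may differ at Day 14 and Month 7. The change should be made, but the primary test is not invalid without it.

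**What to change.** Keep the Mann–Whitney test as the stated primary analysis, and add the following to sections 10.1 and 10.2:

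- At Day 0, Day 14 and Month 7, fit an ANCOVA of the score on group and pre-test with robust standard errors, in the same students as the unadjusted test. Report the adjusted difference in points with its 95% CI.
- At each time point, fit a rank ANCOVA with the same terms as a fixed check. Report it always, and do not make it conditional on a look at skewness.
- Date the additions. Because the analysed numbers already stand in section 7, label these analyses supportive and post hoc, unless it can be shown that they were specified before the data were seen.

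The cost is two extra linear models per time point (six in all) and a short piece of SAP text. No new data are needed. Added at this stage, the models can support the primary result but cannot replace it.

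### Do the between-group Mann–Whitney tests need stratification by university, given that simple randomisation does not balance the two sites?

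*Combined protocol and SAP*

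**What the plan says.** Section 3 places the study in "Midwifery departments of two Turkish universities". Section 8 describes allocation as "Simple randomisation (1:1) using computer-generated list by independent statistician" and mentions neither strata nor blocks. Section 10.1 gives the primary analysis as "Between-group comparison (Day 0): Mann–Whitney U test", and section 10.2 gives the later comparisons as "Between-group at Day 14 & Month 7: Mann–Whitney U". Section 7 reports "Final analysed: Game=39; Control=40". No section plans an analysis by university or a count of students by university and arm.

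**The concern.** In a two-centre trial, stratifying by centre in both the allocation and the analysis is common, so its absence is noticeable. Simple randomisation of about 80 students can leave one arm with more students from the stronger department. If the departments differ in test score, that imbalance moves the estimate in the one trial actually run, and a pooled Mann–Whitney test does not correct for it. The site difference also stays in the error variance and costs power. Had this invalidated the test, all three between-group comparisons (Day 0, Day 14 and Month 7) would have been affected.

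**Working it through.** **Inputs.** From section 7: a Day 0 difference of 40.5 − 37.8 = 2.7 points, SDs of 4.2 and 5.1, and 39 and 40 students analysed. From section 6: a score range of 0–47. The documents give neither the number of students per university nor the score difference between universities. Both are assumptions here: splits of 40/39 and 55/24, and site differences D from 0 to 4 points.

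**The plan's own figure.** Section 7 states "two-sided Mann–Whitney U, power=0.80 required n=35 per group". The usual normal approximation gives n = 2 × (1.960 + 0.842)² × [(4.2² + 5.1²)/2] / 2.7² = 2 × 7.849 × 21.825 / 7.29 ≈ 47 per group, or 50 after dividing by the Mann–Whitney efficiency 3/π. The stated 35 is therefore not recovered. That is a separate matter. It explains why the powers below are near 70% and not 80%, but it does not bear on pooled versus stratified testing.

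**How often the arms differ in site mix.** With arms fixed at 39 and 40, the number from one university in the game arm is hypergeometric. For a 40/39 split, the gap in site share reaches 20 percentage points in 7.3% of allocations; the mean absolute gap is 9 points and its SD is 11.3 points. For a 55/24 split, a gap of 20 points or more occurs in 5.3%. For unrestricted simple randomisation of 80 students, 40 per university, it occurs in about 9%.

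**What a gap does to the estimate.** The shift is gap × D, and the standard error is √(4.2²/39 + 5.1²/40) = 1.05.
- Gap of 20 points: 0.20 × 2 = 0.4 points at D = 2, and 0.20 × 4 = 0.8 at D = 4.
- Mean gap of 9 points at D = 2: 0.09 × 2 = 0.18 points, about 0.17 of a standard error.

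**Why the pooled test stays valid.** If the pilot SDs describe all students together, the site difference is already part of the variance that gives the 1.05. The share of sampling variance due to chance site mix is 0.113² × D² / 1.05². That is 0.0128 × 4 / 1.1025 = 4.6% at D = 2 and 0.0128 × 16 / 1.1025 = 18.6% at D = 4. It is counted, not ignored.

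**Simulation.** 100,000 trials per cell, 40/39 split, total SD held at the pilot values, scores rounded and capped at 47. The comparison is the pooled Mann–Whitney test against a van Elteren test stratified by university.

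| D (points) | Pooled type I error given gap ≥ 20 points | Power pooled / stratified |
|---|---|---|
| 0 | 5.6% (noise, see below) | 69.8 / 68.6% |
| 1 | 5.7% | 69.5 / 69.0% |
| 2 | 7.0% | 69.7 / 70.6% |
| 3 | 9.3% | 69.3 / 73.0% |
| 4 | 13.4% | 69.1 / 77.2% |

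Over all allocations, type I error is 5.0–5.1% pooled and 4.9–5.1% stratified. The 5.6% at D = 0 is Monte Carlo noise: with no site difference the site labels are irrelevant, so the true conditional rate equals the overall rate. About 7,300 runs meet the condition, giving a Monte Carlo standard error of √(0.05 × 0.95 / 7,300) = 0.26 percentage points.

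**The other side of the conditional rates.** If the overall rate is 5.0% and 7.3% of allocations carry the raised rate, the remaining 92.7% must lie below 5%. At D = 4 they average (5.0 − 0.073 × 13.4) / 0.927 = 4.3%; at D = 2, (5.0 − 0.073 × 7.0) / 0.927 = 4.8%. In most allocations the pooled test is slightly conservative.

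**The case for a change.** The strongest opposing case is conditional. A reader has one realised trial, not the average over all possible ones. If its arms happened to differ by 20 points or more in site mix and the universities differed by 3–4 points, the pooled test would reject a true null in 9–13% of such trials, while a stratified test would stay at about 5%. Stratifying would also gain about 4–8 points of power at those site differences. If the site variance is added to the pilot SDs instead of being contained in them, the gain is 0–2 points of power at a difference of 2.35 points (0.5 SD) and 7–9 points at 4.7 (1 SD). The extra test costs little.

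The arithmetic stands, but it depends on a large site difference that nothing in the documents indicates. A 4-point gap between universities would exceed the 2.7-point treatment effect in the pilot. Section 4 limits entry to students in the same year who have passed the same course and have had no breech teaching, and under section 5.2 one investigator gives the lecture with matched content. These features do not prove that the sites are equal, but they give no reason to expect a large difference.

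One modest part remains: a table of students by university and arm would let readers see the balance achieved. That is a reporting courtesy, possible only if university was recorded beside the codes that section 9 describes. It changes no planned result.

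**Conclusion.** The concern does not hold. Simple randomisation followed by a pooled Mann–Whitney test is a coherent pair: unbiased on average, with type I error of about 5% at every site difference examined from 0 to 4 points. Under the fixed-total-SD assumption, stratifying by university changes power by −1.2 points at no site difference, −0.5 at 1 point, +0.9 at 2, +3.7 at 3 and +8.1 at 4. Material gains thus need a site difference larger than the pilot treatment effect. Because section 7 already reports final analysed numbers, a stratified test added now would be a post hoc sensitivity analysis beside an unchanged primary test. The conclusion on validity rests on the randomisation in section 8 having been carried out as described. The sizes rest on assumed site splits and site differences, since the documents give neither.
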